#### 8.4.3.3 *Disease Control Rate*

Disease Control Rate (DCR) is defined as the summed percentage of patients with CR, PR and stable disease (SD) according to RECIST v1.1 per investigator criteria documented at least 8 weeks following treatment initiation.

#### 8.4.3.4 *Patient Reported Outcomes*

Patient-reported outcomes (PRO) for the NCCN-FACT FKSI-19 (Version 2) will be summarized by treatment group. Summary statistics (mean, SD, median, range) of the change from baseline will be provided. Mean score for each endpoint will be displayed graphically. The analysis will be performed for patients in the PRO-evaluable population, which is defined as ITT with a non-missing baseline assessment and at least one non-missing post-baseline assessment until treatment discontinuation.

With the exception of the VAS score and index score for EQ 5D-5L questionnaire, descriptive statistics summarizing the proportions of patients who reported having “no,” “slight,” “moderate,” “severe,” or “extreme/unable” problems at each time point will be reported. The VAS score and the US specific Index score for EQ 5D-5L questionnaire will be summarized and analyzed as continuous measures. Patients without post-baseline assessments will be excluded from this analysis. EQ-5D-5L data will not be reported in the CSR.

#### 8.4.3.5 *Subgroup Analyses*

The consistency of PFS results in subgroups will be examined in the populations where PFS benefit has been demonstrated. To assess the consistency of the study results in subgroups defined by demographics (e.g., age, sex, and race/ethnicity), baseline prognostic characteristics (e.g., KPS performance status, number of previous TKI therapies, MSKCC prognostic criteria, prior anti-PD-1/PD-L1 immunotherapy, etc.), on study proton pump inhibitors, nivo/ipi and nivo use, number of prior lines, and the duration of PFS in these subgroups will be examined. Summaries of PFS, including unstratified HRs estimated from Cox proportional hazards models and Kaplan-Meier estimates of median PFS, will be produced separately for each level of the categorical variables for the comparisons between treatment arms and displayed in a forest plot (**Error! Reference source not found.**).

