- f. Chronic treatment with corticosteroids or other immunosuppressive agents except (i) inhaled or topical steroids or replacement dose corticosteroids equivalent to ≤ 10 mg prednisone and (ii) patients receiving physiological doses of hydrocortisone for adrenal insufficiency
- g. Requirement for continued proton pump inhibitor use after randomization
- h. Any condition including social, psychiatric or medical (including uncontrolled significant concurrent illness) that in the opinion of the Investigator could interfere with treatment or protocol-related procedures
- i. Patients who are pregnant or lactating

PROTOCOL DETAILS

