Preliminary PK data generated in single agent Phase 1 studies indicate that concomitant use of proton pump inhibitors (PPIs) may reduce absorption of CB-839, resulting in decreased systemic exposure. Discontinuation of PPIs is required for patients on study. Alternative antacids such as H2 blockers (e.g., ranitidine, famotidine) and buffering agents (e.g., sodium bicarbonate, calcium carbonate, and sucralfate) may be substituted for PPIs; however to aid absorption, CB-839 should be taken 2 hours before antacid therapy.

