10.2 Randomization

Patients eligible after completing all screening evaluations will be randomly assigned in a 2:1 ratio to receive CBE or PboE.

Randomization will be stratified by the following factors:

- Number of prior VEGFR-targeting TKI therapies: 1 vs. >1
- Number of risk factors per Memorial Sloan-Kettering Cancer Center prognostic criteria for previously treated patients with RCC ([Motzer 2004](#)): favorable vs. intermediate/poor risk

Randomization should occur as close as possible to the planned start of treatment (ie, within 24 hours prior if practicable but no more than 3 days). Patients are defined as enrolled in the study if randomized. Patients who signed consent and are screened but never randomized are screen failures.

Crossover between treatment arms will not be allowed.

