10.6.7 Tumor Assessments

Radiographic response and disease progression will be determined using RECIST version 1.1 and should employ diagnostic quality CT with intravenous contrast or MRI scans (see [Attachment 5](#) for methods of assessment discussion of CT and MRI).

Radiographic tumor assessments will include Chest/ Abdomen/ Pelvis (CAP). Diagnostic quality CT (or MRI) of chest/abdomen/pelvis with intravenous contrast will be performed for all patients at screening, every 8 weeks (± 5 days) from C1D1 for the first 12 cycles, and every 12 weeks (± 7 days) beyond 12 cycles on study. For patients deemed intolerant of intravenous CT contrast, a non-contrast CT of the chest may be obtained along with a contrast enhanced MRI of the abdomen and pelvis.

To ensure image consistency, the same imaging modality and acquisition protocols used at screening should be used for subsequent tumor assessments.

For the purpose of patient management and treatment decisions, radiographic response and disease progression will be assessed by investigators using RECIST v1.1 ([Attachment 5](#)).

Investigators are encouraged, if any doubt or ambiguities exist about radiographic progression, to continue study therapy if the patient is tolerating treatment, and repeat radiographic studies at the next scheduled time, and delay determination of progression until the findings indicating radiographic progression are unequivocal.

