### 8.4 Efficacy Analysis

#### 8.4.1 *Primary Analysis of Progression-Free Survival*

Progression free survival is defined as the time from randomization to the first occurrence of disease progression as determined by the investigator using RECIST v1.1 or death from any cause, whichever occurs first. Patients who have not experienced disease progression or death at the time of analysis will be censored at the time of the last tumor assessment. Additional censoring applies for missing scans. The duration of primary analysis of PFS will be censored as outlined in **Table 2**. A sensitivity analysis will be

performed by handling patients having a PFS event at any time by data cutoff as an event regardless of missing scans. See **Table 3** for details for censor/event rules for PFS sensitivity analysis.

Treatment comparisons will be based on the stratified log-rank test in the ITT population. The stratification factors will be those used for randomization and will be obtained from the IxRS (MSKCC and number of prior therapies with TKI). A 1-sided log-rank  $p < 0.2$  in favor of the CBE experimental treatment will be regarded as a positive result. The null and alternative hypotheses can be phrased in terms of the survival functions  $S_{PFS\_CBE}(t)$  and  $S_{PFS\_PboE}(t)$  in arm CBE and arm PboE, respectively:

$$H_0: S_{PFS\_CBE}(t) = S_{PFS\_PboE}(t) \text{ versus } H_1: S_{PFS\_CBE}(t) > S_{PFS\_PboE}(t)$$

Kaplan-Meier methodology will be used to estimate median PFS for each treatment arm and construct survival curves for the visual description of the difference between the treatment arms. The Brookmeyer-Crowley methodology will be used to construct the 95% CI for the median PFS for each treatment arm (1).

The hazard ratio (HR),  $\lambda_{PFS\_CBE}/\lambda_{PFS\_PboE}$ , where  $\lambda_{PFS\_CBE}$  and  $\lambda_{PFS\_PboE}$  represent the hazard of PFS in arm CBE and arm PboE, respectively, will be estimated with a stratified Cox regression model and the same stratification variables used for the stratified log-rank test. To prevent a stratification cell having too few events, if a stratification cell has less than 10 PFS events (two arms combined), the stratification factor that contributes the least number of events for that cell will be removed. Stratification factors for the analyses will be removed until all stratification cells have at least 10 PFS events in two arms combined.

Results from an unstratified analysis will also be provided.

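### On-study PPI use is a fixed PFS subgroup with no exposure window; if PPI starts continue well into follow-up, the per-level medians carry immortal time in favour of users

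*SAP*

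**What the plan says.** SAP 8.4.3.5 names demographic and baseline prognostic subgroups and then adds "on study proton pump inhibitors, nivo/ipi and nivo use, number of prior lines, and the duration of PFS in these subgroups will be examined". Unstratified Cox hazard ratios and Kaplan-Meier medians "will be produced separately for each level of the categorical variables for the comparisons between treatment arms", shown in a forest plot. The section applies only to populations in which a PFS benefit has been shown. SAP 8.4.1 sets the time origin: "Progression free survival is defined as the time from randomization to the first occurrence of disease progression".

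Protocol 10.1.1 gives the likely reason for the PPI row: "concomitant use of proton pump inhibitors (PPIs) may reduce absorption of CB-839, resulting in decreased systemic exposure". It adds "Discontinuation of PPIs is required for patients on study", and Protocol 8.2 excludes patients with "Requirement for continued proton pump inhibitor use after randomization".

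Start and stop dates of concomitant drugs are recorded (Protocol 10.1.1), from consent until 28 days after treatment stops (Protocol Attachment 1). That is a data-collection period, and nothing ties it to the subgroup. Neither document gives the subgroup an exposure window, a landmark, a time-dependent term or a start-date rule, and neither says when on-study use would begin.

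Scans are due "every 8 weeks (± 5 days) from C1D1 for the first 12 cycles" (Protocol 10.6.7). Randomisation precedes C1D1, "within 24 hours prior if practicable but no more than 3 days" (Protocol 10.2).

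**The concern.** The other listed factors of this kind, such as age, sex, risk group and prior lines, are known at randomisation. On-study PPI use may not be. Someone whose PPI starts in month 5 had to be free of progression and alive for five months to enter the user level, yet those months count as user PFS. Someone who progresses in month 2 before needing a PPI is a non-user. This is immortal-time bias: it lengthens the user median and shortens the non-user median even if the drug does nothing.

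What is at stake is how the row is read. Because the protocol says PPIs may lower CB-839 exposure, a reader will look at CBE users and ask whether they did worse. Immortal time pushes against that signal and could hide a real loss of effect, or under some start patterns reverse it. The undefined window also leaves the grouping to be settled after unblinding.

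**Working it through.** **1. The plan's own figure.** The documents give no number for the PPI row. The design inputs (SAP 6.2, Protocol 14.5) are a control median of 3.7 months, HR 0.60, 2:1 allocation, one-sided alpha 0.2, power 0.80, 8 months of accrual and 6 of follow-up. Required events = (0.8416 + 0.8416)² / [(2/9) × (ln 0.60)²] = 2.833 / (0.2222 × 0.2609) = 48.9, against the stated 48. The inputs hang together, so I use them.

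**2. Mechanism.** Under exponential PFS with median m, patients event-free at a PPI start time d have median d + m from randomisation. The CBE median is 3.7/0.60 = 6.17 months, so an inert PPI started at 2 months gives users 2 + 6.17 = 8.17. With d = 0 there is no shift.

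**3. Simulation.** Start patterns are assumptions. A user is a patient whose PPI starts before the PFS event or censoring. The PPI is either inert or returns the CBE hazard to the control hazard from its start. Cutoff is 14 months (8 + 6). *Continuous* means progression is seen at once (1,000,000 patients per scenario). *Scans* means progression is dated at the next scheduled scan (every 56 ± 5 days for 12 cycles, then every 84; randomisation 0–3 days before C1D1; 0% or 15% of events are deaths dated exactly; censoring at the last scan; 600,000 patients). Entries are CBE user vs non-user medians in months.

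| Assumed starts | Inert, continuous | Inert, scans | Effect abolished, continuous | Effect abolished, scans |
|---|---|---|---|---|
| From baseline, 5–15% of patients | 6.2 vs 6.2 | 7.3 vs 7.3 | 3.7 vs 6.2 | 3.9 vs 7.3 |
| Within 1–2 months, 10–20% | 6.7–7.2 vs 5.9–6.1 | 7.3 vs 7.3 | 4.2–4.7 vs 6.0–6.1 | 5.4–5.5 vs 7.3 |
| Over 4 months, 10–20% | 8.1 vs 5.8–6.0 | 7.5 vs 6.4–7.3 | 5.7 vs 5.8–6.0 | 5.7 vs 6.7–7.3 |
| Over 6 months, 10–20% | 9.0 vs 5.6–5.9 | 9.1 vs 5.8–7.3 | 6.7 vs 5.6–5.9 | 7.3 vs 5.8–7.3 |
| Continuing at 2–10% per month | 10.0–10.8 vs 3.9–5.6 | 9.3 vs 5.5–5.8 | 7.4–8.2 vs 3.9–5.6 | 7.4–7.6 vs 5.5–5.8 |

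The scan columns are the relevant ones. The first scan falls at about 56/30.4375 = 1.84 months, so few patients can have an event before a start in the first two months. Scan-based medians also move in steps of about 1.8 months and can jump a step near a boundary: at 2% per month with no deaths, the inert non-user median was 7.2 in one run rather than 5.8. The 12-month restricted means are smoother. With an inert PPI they are 7.0–7.1 vs 6.9–7.1 for starts within 1–2 months and 8.4–8.7 vs 5.9–6.8 for continuing starts. For starts over 6 months with the effect abolished they are 7.1 vs 6.9–7.0.

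**4. Planned between-arm HRs, 14-month cutoff.** Inert PPI: 0.56–0.60 in users and 0.60–0.66 in non-users, against 0.60. Effect abolished, with scans: 0.82–1.01 and 0.60–0.65, against 1.00 and 0.60. At 5% per month users have about 4.95 CBE and 2.68 PboE events, so SE(log HR) = √(1/4.95 + 1/2.68) = 0.76. The largest user shifts, ln(0.56/0.60) = −0.07 and ln 0.82 = −0.20, are small beside that.

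**5. Effect of the missing window.** In continuous time, counting starts up to 28 days after the PFS event as use changes the inert continuing-start medians from 10.0–10.8 vs 3.9–5.6 to 9.1–9.9 vs 4.0–5.7.

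**6. Confounding by indication.** The models above omit it. In a separate continuous-time check (control arm, 30% of patients due to start over 4 months, no PPI effect, no cutoff), users vs non-users are 5.6 vs 3.1 with no confounding, 3.6 vs 2.8 if starters have twice the hazard, and 2.7 vs 2.6 at three times.

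**The case against.** The SAP compares arms within each level and plans no user versus non-user contrast; that comparison is the reader's own step, and the planned HRs barely move. The protocol excludes continued PPI need, requires discontinuation and offers alternative antacids, so a steady stream of new starts is not the obvious expectation. Use carried over from before randomisation has no immortal time. Numbers are tiny: at 5% per month there are about 10 CBE users with about 5 events, and with 42 CBE patients the user median was not reached in about 30% of simulated trials (21% with scans). If starters are sicker, the direction may be offset.

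All of this stands and limits the point. It does not remove it, because per-level medians are a planned output and the level is undefined.

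A reader might infer more: that any start after randomisation distorts the medians, or that CBE users would look better whenever PPIs remove the drug effect. The documents support neither. Under the 8-weekly schedule, starts within 2 months leave inert medians level, and starts within 4 months keep a true loss of effect in the right direction. Starts over 6 months mostly hide it, and only continuing starts clearly reverse it. Nor is the primary analysis affected.

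**Conclusion.** The point holds as a minor flaw in an exploratory display. SAP 8.4.3.5 treats a status that can arise after randomisation as a fixed level, with PFS counted from randomisation and no window. If PPI starts continue well into follow-up, the user median is inflated: with an inert PPI by about 9.3 − 7.3 = 2 months for continuing starts under the trial's scans, while the non-user median falls. If starts are early or carried over, there is little or no distortion.

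The size rests on assumed start patterns, exponential PFS with the plan's medians, a 14-month cutoff and starts independent of prognosis. SAP 6.3 expects the analysis at about 20 months; in continuous time that cutoff widens the inert continuing-start gap to 10.8–12.2 vs 3.4–5.4 and leaves early starts unchanged. With about 63 patients, any user median will be very imprecise.

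**What to change.** Remove ever/never on-study PPI use from the fixed-level subgroups and the forest plot, keeping there only factors fixed at or before randomisation. Define exposure as PPI use that overlaps CB-839/placebo dosing and starts before the PFS event or censoring. Report it as an exploratory listing or descriptive summary.

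Add a time-dependent PPI covariate, or a landmark, only if the number of exposed events allows. A landmark should follow the first-scan window: 56 + 5 + 3 = day 64 from randomisation. It would have about 48–49 of 63 patients at risk, about 2–10 exposed and about 1–7 exposed events (SE of log HR about 0.8–2.0), so it should not be the main remedy.

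The cost is SAP wording and one listing or table. Recorded dates run to 28 days after treatment stops, which covers a window limited to dosing, so no new data are needed. They would not cover a window running to the PFS event in patients who stop treatment without progression and stay in imaging follow-up (Protocol 10.4). The downsides are low precision and confounding by indication, which no option removes.

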### 8.5 **Pharmacokinetic Analyses**

PK analyses will be performed for the PK-evaluable population, defined as all CBE patients who have received at least one dose of CB-839 and at least one evaluable PK sample. CB-839 serum concentration data ( $C_{\min}$  and  $C_{\max}$ ) will be tabulated and summarized. Descriptive statistics will include means, medians, ranges, and SDs, as appropriate.

## **8.6 Safety Analyses**

Unless specified otherwise, safety analyses described in this section will be conducted for the Safety population, with patients grouped according to whether they received any CB-839 treatment.

### **8.6.1 Exposure of Study Medication**

Study drug exposure statuses, which include treatment duration, total dose received (mg), number of cycles, dose intensity (mg/day), and relative dose intensity (%), will be summarized for each treatment arm for the Safety population.

### **8.6.2 Adverse Events**

Verbatim description of AEs will be mapped to Medical Dictionary for Regulatory Activities (MedDRA, v19.1) preferred terms and system organ classes, and graded by the investigator according to NCI CTCAE v4.03. Treatment-emergent adverse events (TEAEs) will be summarized by mapped term, appropriate thesaurus level, NCI CTCAE grade, and treatment arm. In addition, serious adverse events, severe adverse events (Grade  $\geq 3$ ), and adverse events leading to study drug discontinuation or interruption will be summarized accordingly. Multiple occurrences of the same event will be counted once at the maximum grade. All deaths are reported as SAEs per study conduct. In order to accurately summarize the true SAE rate, all SAE summaries will not count grade 5 events for patients who died due to progressive disease.

For reporting purposes, “treatment emergent” is defined as adverse events occurring on or after the first dose of study drug is administered until the clinical cutoff date, or existing events that worsened after the first dose during the study.

All listings of adverse events will also include all adverse events.

Deaths reported during the study treatment period and the follow-up period after treatment completion and/or discontinuation will be listed by treatment arm.

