Table 9.5-2: CB-839 Related Adverse Events in $\geq 5\%$ of Patients Treated with Monotherapy CB-839 on the BID Schedule on Study CX-839-001
BID Schedule - Monotherapy (N=88): CB-839 Related TEAEs

MedDRA Preferred Term	Number (%) of patients	
	All Events	\geq Grade 3 [^]
Patients with Any CB-839-Related TEAE	61 (69.3)	3 (3.4)
FATIGUE	21 (23.9)	0
NAUSEA	20 (22.7)	0
ALANINE AMINOTRANSFERASE INCREASED	13 (14.8)	2 (2.3)
PHOTOPHOBIA	12 (13.6)	0
ASPARTATE AMINOTRANSFERASE INCREASED	10 (11.4)	1 (1.1)
DECREASED APPETITE	7 (8.0)	0
GAMMA-GLUTAMYLTRANSFERASE INCREASED	7 (8.0)	2 (2.3)
BLOOD ALKALINE PHOSPHATASE INCREASED	6 (6.8)	1 (1.1)
VOMITING	5 (5.7)	0

[^]no Grade 4 or Grade 5 events

Photophobia and related ocular toxicities (e.g., photopsia) have been identified as CB-839-related events. In all but one case, these events have been Grade 1 and without impact on patients' daily lives. One photophobia event was characterized as Grade 2 and required the patient rest for 1-2 hr in a dark room. These events appear to occur around C_{max} (1-4 hr after dosing) and resolve with time. Anecdotal reports suggest that these events tend to become less frequent over extended dosing. The AE profile of monotherapy CB-839 using the original schedule (TID without food) as well as the final schedule (BID with food) are described more completely in the Investigator's Brochure.

CB-839 + Everolimus

The combination of CB-839 with everolimus has been well tolerated to date. The frequency of adverse events (reported as of the safety data cut of 23 January 2017) in patients receiving CB-839 on the BID regimen in combination with standard dose everolimus (10 mg QD orally) are provided in [Table 9.5-3](#) (all adverse events) and [Table 9.5-4](#) (treatment related adverse events). Of the first 19 patients who have received escalating doses of CB-839 (7 at 400 mg, 9 at 600 mg and 3 at 800 mg orally BID with food) in combination with everolimus, the most frequent AEs were anemia, decreased appetite, creatinine increase and hyperglycemia; with anemia,

hyperglycemia and fatigue being the most frequent Grade 3/4 AEs. Of note, both patients with G3 hyperglycemia had preexisting diabetes (Table 9.5-3).

Table 9.5-3: Adverse Events in ≥ 3 Patients Treated with CB-839 + Everolimus on Study CX-839-001

CB-839 + Everolimus (N=19): All TEAEs		
MedDRA Preferred Term	Number (%) of patients	
	All Events	\geq Grade 3
Patients with Any TEAE in CBE Cohort	19 (100.0)	13 (68.4)

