ANAEMIA	13 (68.4)	5 (26.3)
DECREASED APPETITE	9 (47.4)	0
BLOOD CREATININE INCREASED	7 (36.8)	0
HYPERGLYCAEMIA	7 (36.8)	2 (10.5)*
COUGH	6 (31.6)	0
NAUSEA	6 (31.6)	0
DIARRHOEA	5 (26.3)	1 (5.3)
HEADACHE	5 (26.3)	1 (5.3)
PROTEINURIA	5 (26.3)	0
VOMITING	5 (26.3)	0
ASPARTATE AMINOTRANSFERASE INCREASED	4 (21.1)	0
FATIGUE	4 (21.1)	2 (10.5)
STOMATITIS	4 (21.1)	0
ABDOMINAL PAIN	3 (15.8)	1 (5.3)
ALANINE AMINOTRANSFERASE INCREASED	3 (15.8)	0
CHILLS	3 (15.8)	0
DERMATITIS ACNEIFORM	3 (15.8)	0
DYSGEUSIA	3 (15.8)	0
DYSPNOEA	3 (15.8)	0
HYPOMAGNESAEMIA	3 (15.8)	0
HYPOPHOSPHATAEMIA	3 (15.8)	1 (5.3)
INSOMNIA	3 (15.8)	0
MUCOSAL INFLAMMATION	3 (15.8)	0
MYALGIA	3 (15.8)	1 (5.3)
PAIN	3 (15.8)	1 (5.3)
PLATELET COUNT DECREASED	3 (15.8)	0
PYREXIA	3 (15.8)	0
THROMBOCYTOPENIA	3 (15.8)	0
WEIGHT DECREASED	3 (15.8)	0

*preexisting diabetes

Treatment-related adverse events that were Grade 3 were few in number and there have been no Grade 4 events (Table 9.5-4). One event of Grade 3 rash occurred at the 400 mg BID dose level, which was considered a dose limiting toxicity (DLT). The rash was considered related to everolimus and resolved upon a dose reduction of everolimus (CB-839 continued at full dose). No additional DLTs have been reported in subsequent patients treated at 400, 600 or 800 mg BID and a maximum tolerated dose has not been identified.

Table 9.5-4: Treatment-Related Adverse Events in ≥ 3 Patients Treated with CB-839 + Everolimus on Study CX-839-001

CB-839 + Everolimus (N=19): Treatment-related TEAEs*		
MedDRA Preferred Term	Number (%) of patients	
	All Events	\geq Grade 3[^]
Patients with Any Treatment-related TEAE in CBE cohort	19 (100)	9 (47.4)
DECREASED APPETITE	7 (36.8)	0
ANAEMIA	5 (26.3)	1 (5.3)
DIARRHOEA	5 (26.3)	0
HYPERGLYCAEMIA	5 (26.3)	2 (10.5)
PROTEINURIA	5 (26.3)	0
ASPARTATE AMINOTRANSFERASE INCREASED	4 (21.1)	0
BLOOD CREATININE INCREASED	4 (21.1)	0
FATIGUE	4 (21.1)	2 (10.5)
NAUSEA	4 (21.1)	0
STOMATITIS	4 (21.1)	0
ALANINE AMINOTRANSFERASE INCREASED	3 (15.8)	0
DERMATITIS ACNEIFORM	3 (15.8)	0
DYSGEUSIA	3 (15.8)	0
MUCOSAL INFLAMMATION	3 (15.8)	0
MYALGIA	3 (15.8)	0
THROMBOCYTOPENIA	3 (15.8)	0
VOMITING	3 (15.8)	0

[^]no Grade 4 or Grade 5 events

*considered to be at least possibly related to either CB-839 or everolimus

Please refer to the most recent CB-839 Investigator's Brochure for additional safety information from the Phase 1 studies.

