11.1.2 Everolimus

Adverse events most frequently observed with everolimus are rash, stomatitis/oral mucositis, fatigue, headache, anorexia, nausea, vomiting, diarrhea, and infections (see everolimus Package Insert). Overall, the most frequently observed laboratory abnormalities include neutropenia, thrombocytopenia, hypercholesterolemia, and/or hypertriglyceridemia. The majority of these AEs have been of mild to moderate severity (CTCAE Grade 1-2). Everolimus has been associated with a low incidence of severe and potentially lethal AEs, including non-infectious pneumonitis, infections, and renal failure (see Warnings and Precautions in the Package Insert). Everolimus dosing and toxicity should be managed according to the Package Insert and local institutional practice.

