14.4 Safety Analysis

Safety will be assessed by the incidence and severity of adverse events (AEs); the analysis will be performed on the Safety Analysis Patient Set as defined in [Section 14.4.2](#).

Adverse events will be coded by System Organ Class (SOC) and Preferred Term (PT) using the Medical Dictionary for Regulatory Activities (MedDRA). The number and proportion of patients reporting a given AE will be tabulated by treatment group according to the worst severity reported. Separate tables will be constructed for a) all reported AE's, b) serious AEs (SAEs), and c) AE's leading to permanent discontinuation of study treatment. The above tables will also be presented for treatment-emergent AEs (TEAEs) judged to be related to the study treatment.

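### No planned adverse event table counts the patients with a toxicity coded to more than one MedDRA preferred term; a short list of grouped terms, fixed before unblinding, would supply it

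*SAP*

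**What the plan says.** SAP 8.6.2 (Adverse Events) maps verbatim terms to MedDRA "preferred terms and system organ classes, and graded by the investigator according to NCI CTCAE v4.03". It then says: "Treatment-emergent adverse events (TEAEs) will be summarized by mapped term, appropriate thesaurus level, NCI CTCAE grade, and treatment arm". Its one within-patient counting rule is: "Multiple occurrences of the same event will be counted once at the maximum grade". Protocol 14.4 works at the same two levels: "Adverse events will be coded by System Organ Class (SOC) and Preferred Term (PT"), with tables by worst severity for all events, serious events and events leading to permanent discontinuation, and again for related events. Neither document defines grouped terms, standardised queries or adverse events of special interest.

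Elsewhere the protocol speaks of some toxicities as families. Section 9.5 says: "Photophobia and related ocular toxicities (e.g., photopsia) have been identified as CB-839-related events". Section 11.1.2 joins stomatitis and oral mucositis in one item: "Adverse events most frequently observed with everolimus are rash, stomatitis/oral mucositis, fatigue, headache, anorexia, nausea, vomiting, diarrhea, and infections". Table 9.5-3, the Phase 1 table for the combination, has these two separate rows: "PLATELET COUNT DECREASED 3 (15.8) 0" and "THROMBOCYTOPENIA 3 (15.8) 0".

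SAP 8.6.3 adds laboratory summaries by arm, including values outside the normal range and selected laboratory data by CTCAE grade. The selected analytes are not named.

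**The concern.** A preferred-term table answers how many patients had a given coded term. A reader who compares tolerability usually wants to know how many patients had a given toxicity. The two differ when sites describe one toxicity in different words and the dictionary keeps those words as separate terms. The counting rule in SAP 8.6.2 removes repeats of the same event. It does not say that different terms for one toxicity are to be combined, so each stays in its own row. Adding the rows double-counts patients who had both terms, and reading the largest row misses patients who had only the other.

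A system organ class total does not solve this, because it also contains unrelated events. The documents do not show whether the paired terms even share a class. An undefined thesaurus level could hold a grouping, but nothing fixes it before the data are unblinded.

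Comparing the safety and tolerability of the two arms is a stated objective (protocol section 5.0). At stake is how clearly the toxicity of the combination is described in about 42 and 21 patients, where rows are already sparse.

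**Working it through.** **Inputs.** Table 9.5-3 (all treatment-emergent events, N=19): platelet count decreased 3, thrombocytopenia 3, stomatitis 4, mucosal inflammation 3. Table 9.5-4 (treatment-related events in at least 3 patients, N=19): thrombocytopenia 3, stomatitis 4, mucosal inflammation 3, hyperglycemia 5, anemia 5; platelet count decreased is not listed. Planned arms: about 42 and 21 (protocol 14.5). No table reports how many patients had both terms of a pair.

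**Step 1, the protocol's own percentages.** 3/19 = 15.8% and 4/19 = 21.1%, as printed.

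**Step 2, bounds on the toxicity count.** If *a* and *b* patients have the two terms, the number with at least one lies between max(*a*, *b*), when overlap is complete, and *a* + *b*, when there is none.

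- Platelets: 3 to 6 of 19, or 15.8% to 31.6%.
- Stomatitis and mucosal inflammation: 4 to 7 of 19, or 21.1% to 36.8%. This assumes that the mucosal inflammation cases were oral, which the table does not say.

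If the two terms occurred independently, the figures would be 1 − (16/19)² = 29.1% and 1 − (15/19)(16/19) = 33.5%. Independence is an assumption, used only to place a value inside the range.

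**Step 3, under-count by the largest row.** This is 1 − max(*a*, *b*)/(number with either term).

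- Platelets: from 1 − 3/3 = 0% to 1 − 3/6 = 50%.
- Stomatitis and mucosal inflammation: from 1 − 4/4 = 0% to 1 − 4/7 = 43%.

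**Step 4, effect on a displayed table.** Tables 9.5-3 and 9.5-4 use the same cutoff of 3 patients. Platelet count decreased drops out of the second, so at most 2 patients had it as a related event. Thrombocytopenia stays at 3. The grouped related count would be 3 to 3 + 2 = 5 patients (15.8% to 26.3%); the table shows only the 3.

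Protocol 11.1.3 names decreased appetite, hyperglycemia and anemia as the most frequent related events. If at most one patient had both mucosal terms, and the cases are one toxicity, the grouped related count would be 7 − 1 = 6 or 7. That is above the 5 for hyperglycemia and the 5 for anemia, but section 11.1.3 does not mention it.

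**Step 5, what grouping does at 42:21.** Assume, for illustration only, a control rate half the combination rate.

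| | CBE | PboE | Expected patients | Difference, 95% half-width | Fisher power (two-sided 0.05) |
|---|---|---|---|---|---|
| Grouped | 31.6% | 15.8% | 13.3 vs 3.3 | 15.8 ± 21 points | 0.22 |
| One row, each rate halved | 15.8% | 7.9% | 6.6 vs 1.7 | 7.9 ± 16 points | 0.08 |

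The comparison is imprecise in both lines. Splitting lowers the visible rates and the visible difference, but it is not the main reason for the imprecision.

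**The case against.** The strongest case against has four parts.

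- **Laboratory tables.** SAP 8.6.3 summarises laboratory values by arm whatever words the site used for the event. Platelets, hemoglobin, and white cells with differential are protocol tests (Attachment 2). The only pair that can reach a one-half under-count is the platelet pair, which is such a toxicity. This stands in part. The graded analytes are not named, and laboratory tables show nothing about photophobia, mucosal toxicity or rash. They also do not carry relatedness, seriousness or discontinuation.
- **Recording rules.** Protocol 15.1 asks for a clinically significant laboratory abnormality to be recorded as a single diagnosis, and 15.2 prefers a specific diagnosis. This limits duplicate entries for one patient. It does not make all sites choose the same term.
- **Evidence.** Adjacent rows do not prove an under-count, since overlap is unreported and the range includes zero. Section 11.1.2 pairs stomatitis with oral mucositis, not with mucosal inflammation. All four rows have no event of Grade 3 or above. All of this stands, so the size must be given as a range, and nothing is shown for severe toxicity.
- **No test, double-blind.** Choice of synonym should not depend on arm, and no safety hypothesis is tested. This also stands. The gain is in description, not in removing a bias between arms.

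A reader might infer that events are counted by preferred term alone. The documents do not support that: system organ class is mapped as well, and a further thesaurus level is mentioned. A reader might also infer that split rows would leave only one or two control patients each. At the Phase 1 rates, 21 patients give 21 × 15.8% = 3.3 and 21 × 21.1% = 4.4. Smaller counts need an assumed lower control rate, which the documents do not give.

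**Conclusion.** The point holds as a cheap improvement, not as an error in the plan. The planned adverse event tables give counts by preferred term and by system organ class. None is specified that gives a patient count for a toxicity coded to more than one preferred term. In the Phase 1 data the largest row under-counts by 0% to 50% for low platelets and by 0% to 43% for stomatitis with mucosal inflammation. Both maxima assume that no patient had both terms, and the second also assumes that the two terms describe one toxicity.

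A reader might infer from the upper bound that key toxicities are in fact under-counted by half. The documents do not support this: one half is the limit for a single pair, the true value may be zero, and that pair is partly covered by the laboratory summaries. Nor do they show that splitting would distort the comparison between arms. Sample size, event count and alpha are unaffected.

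**What to change.** Before unblinding (SAP 8.8 places it at the primary PFS analysis), add to SAP 8.6.2 a short, fixed list of grouped terms, limited to synonyms or closely related terms:

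- thrombocytopenia and platelet count decreased;
- stomatitis, oral mucositis and mucosal inflammation;
- photophobia, photopsia and related visual terms;
- rash terms;
- the synonym pairs for anemia and for neutropenia.

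Count each patient once per group, at worst grade, by arm. Keep the preferred-term and system organ class tables beside the grouped ones, so that a reader can see what each group contains. State in the same section which thesaurus levels will be tabulated, and in SAP 8.6.3 which analytes will be graded. Pooling different liver enzymes is optional, since they are separate analytes and not synonyms.

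The cost is about one page of terms and one extra table per adverse event category, with no new data. Grouping needs some judgement; fixing the list while blinded and keeping the single-term tables limits its influence.
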